6.8.3. Vaccine Efficacy on Duration and Presence/Severity of COVID-19 Symptoms

Subjects will report symptoms including fever (temperature $\geq 38^{\circ}\text{C}$), chills, cough, shortness of breath, difficulty breathing, fatigue, muscle aches (myalgia), body aches, headache, new loss of taste, new loss of smell, sore throat, nasal congestion, runny nose (rhinorrhea), nausea, vomiting, and diarrhea. The severity scoring system of the symptoms is presented in the table below. A score endpoint aggregating duration and presence/severity of COVID-19 symptoms may be calculated as the sum of daily severity scores of all recorded symptoms across all days with symptoms. The VE of mRNA-1273 based on mean score of each treatment group will be calculated as below:

$$\text{VE} = [1 - \text{Mean score of mRNA-1273 group} / \text{Mean score of placebo group}] \times 100\%$$

Table 9: Grading of COVID-19 Symptoms

Grading	All Symptoms	For Nausea/Vomiting ONLY	For Sense of Smell/Taste ONLY	Score
None	No symptom			0
Mild	I had the symptom, but I could still do my normal activities	I was able to eat and drink normally	I had the symptom, but I retained some taste/smell	1
Moderate	The symptom really bothered me. It was hard to do my normal activities.	It bothered me enough that I did not eat or drink normally.	My taste/smell was significantly affected.	2
Severe	The symptom was very bad. I was not able to do activities that I usually do.	I could not eat or drink.	I have no taste or smell.	3

A proportional means model including vaccination group as fixed effect and stratified with stratification factor at randomization will be used to assess the VE (mRNA-1273 vs. placebo) on the score aggregating duration and presence/severity of COVID-19 symptoms based on the PP Set. The score will be summarized and categorized into quartiles (across the two groups) using 1, 2, 3, 4. The indication of the quartiles will be used as the dependent variable in the proportional mean model.

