If the symptoms persist after Day 60, then telemedicine calls can be reduced to weekly; however, the participant should still report the daily symptoms at that contact.

Telemedicine visits may be conducted by videoconference or by audio only (telephone). During the telemedicine visit (preferably done in the evening), the participant will be asked to verbally report the severity of each symptom and their highest body temperature and lowest oxygen saturation for that day, and the investigator will determine if medical attention is required due to

worsening of COVID-19 symptoms. The presence and severity of each symptom reported by the participant will be noted in the appropriate source document ([Table 19](#)).

During the telemedicine visits, participants will be reminded both to collect their own saliva sample on 3, 5, 7, 9, 14, and 21 days after the initial Illness Visit and to return the sample to the study site. Immediately upon receipt of a saliva sample, the study site will send it for testing to the study central virology laboratory.

During the telemedicine visits, if the participant has a positive result for SARS-CoV-2 from the Day 1 Illness Visit, the participant will continue the Convalescent Period. If the participant has a negative result for SARS-CoV-2 from the Day 1 Illness Visit, the participant will exit the Convalescent Period, including discontinuation of daily telemedicine visits and collection of saliva samples, and will return to their respective study schedule ([Table 16](#), [Table 17](#), [Table 18](#), or [Table 23](#)). Participants who are pending a central laboratory PCR may exit from the Convalescent Period based on a negative PCR result from a CLIA-certified or CLIA-certified waiver local laboratory, at the investigator's discretion. However, if the central laboratory PCR results are positive after exit from the Convalescent Period, the Convalescent Period must resume.

All participants confirmed to be COVID-19 cases will be scheduled for a Convalescent Visit (study site or home visit) 28 days after the initial Illness Visit. At this visit, a saliva sample will be collected and a blood sample will be drawn for immunologic assessment of SARS-CoV-2 infection ([Table 19](#)).

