9.3. Sample Size Determination

The sample size is driven by the total number of cases to demonstrate VE (mRNA-1273 vs. placebo) to prevent COVID-19 in Part A. Under the assumption of proportional hazards over time and with 1:1 randomization of mRNA-1273 and placebo, a total of 151 COVID-19 cases will provide 90% power to detect a 60% reduction in hazard rate (60% VE), rejecting the null hypothesis H_0 : VE $\leq 30\%$, with 2 IAs at 35% and 70% of the target total number of cases using a 1-sided O'Brien-Fleming boundary for efficacy and a log-rank test statistic with a 1-sided false positive error rate of 0.025. The total number of cases pertains to the PP Set accruing at least 14 days after the second dose. There are 2 planned IAs in this study, which will be performed when approximately 35% and 70% of the target total number of cases have been observed. Approximately 30,000 participants will be randomized with the following assumptions:

- The target VE against COVID-19 is 60% (with 95% CI lower bound ruling out 30%, rejecting the null hypothesis H_0 : VE $\leq 30\%$)
- A 6-month COVID-19 incidence rate of 0.75% in the placebo arm
- An annual dropout rate of 2% (loss of evaluable participants)
- Two IAs at 35% and 70% of total target cases across the 2 treatment groups with O'Brien-Fleming boundaries for efficacy monitoring
- 3-month uniform accrual
- Approximately 15% of participants will be excluded from the PP population, and participants are at risk for COVID-19 starting 14 days after the second dose

[Table 6](#) provides sample size with 90% power to demonstrate VE on COVID-19.

Table 6: Conditions and Sample Size to Demonstrate Vaccine Efficacy

Target VE	Lower Bound	Randomization Ratio	Total # of Cases	6-Month Incidence Rate		Total Sample Size ^a
				Placebo	mRNA-1273	
--	--	--	--			--
60%	30%	1:1	151	0.75%	0.30%	30,000

Abbreviations: IP = investigational product; PP = Per Protocol; VE = vaccine efficacy.

[figure not shown]
^a Sample size to account for 15% participants to be excluded from the PP Set (eg, seropositive at baseline, have not received planned IP).

The sample size is calculated using R package gsDesign ([Anderson 2020](#)).

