6.8.1. Vaccine Efficacy Against Burden of Disease

Exploratory analysis of BOD due to COVID-19 will be performed. A BOD score is defined based on the post SARS-CoV-2 infection follow-up to reflect the worst severity of symptoms as shown in the table below.

Table 7: Burden of Disease Score

Subject State (Worst Category Following Disease Detection)	BOD Score
Without COVID-19 (uninfected/asymptomatic infection)	0
COVID-19 without hospitalization (symptomatic without hospitalization)	1
COVID-19 with hospitalization	2
Death	3

Summary of BOD score, number and percentage of subject with each level of BOD score, will be provided by treatment group using the PP Set. A t-test of the BOD scores may be performed to compare mRNA-1273 vs. placebo group.

To assess impact of baseline risk of severe disease on the vaccine effect regarding disease severity, summary of BOD may be provided by randomization strata (i.e. ≥ 65 years, < 65 years at risk, and < 65 years not at risk).

In order to assess the disease burden in subjects with COVID-19, the above analyses may also be performed in participants with COVID-19, i.e. subjects with BOD score of zero will be excluded from the analysis.

While transparent, the proportions in the summary table will change with increased follow-up time as more subjects inevitably acquire disease. This makes comparisons across

different periods of follow-up difficult. To augment this analysis, a proportional means model will be used to assess the treatment effect on BOD between mRNA-1273 and placebo in terms of ratio of mean severity score. The proportional means model allows for direct comparisons across different periods of follow-up, unaffected by differential follow-up. A proportional means model including vaccination group as fixed effect and stratified with stratification factor at randomization will be used to assess the vaccine effect on BOD. The VE for the BOD score will be estimated as 1 minus the ratio of means as estimated by the proportional means model and reported with 95% confidence intervals.

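### SAP Part A 6.8.3 codes the symptom score by pooled quartiles 1 to 4 on the PP Set with no zero category; as written, the code reduces to case versus non-case and pulls the model's VE toward 0

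*SAP*

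**What the plan says.** SAP Part A 6.8.3 defines a symptom score as "the sum of daily severity scores of all recorded symptoms across all days with symptoms". Each symptom-day is graded 0 to 3 (Table 9 of that SAP), so a participant with no recorded symptoms has an empty sum, which is 0.

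The section then gives two analyses on different scales:

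- A direct formula on the raw score: "The VE of mRNA-1273 based on mean score of each treatment group will be calculated as below", namely one minus the ratio of the two group means.
- A stratified proportional means model assessing VE "on the score aggregating duration and presence/severity of COVID-19 symptoms based on the PP Set". For this model, "The score will be summarized and categorized into quartiles (across the two groups) using 1, 2, 3, 4", and "The indication of the quartiles will be used as the dependent variable in the proportional mean model".

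Nothing in 6.8.3 limits the quartiles to COVID-19 cases or to positive scores. It names no code for a score of 0 and no rule for ties. The two preceding sections are more explicit. Tables 7 and 8 give unaffected participants a score of 0, and 6.8.1 writes out its case-only analysis: "subjects with BOD score of zero will be excluded from the analysis".

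Protocol 9.5.1.1 promises an analysis that takes symptom duration and severity into account and leaves the details to the SAP. Section 6.8.3 is where those details are given.

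**The concern.** Quartiles form four groups only if the variable is spread across the population in which they are cut. Here that population is the whole PP Set, and almost everyone in it has the same value, 0. A cut made as written cannot rank cases by symptom burden, which is the purpose of the analysis.

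The lowest code adds a second problem. A ratio of means is informative when unaffected people contribute 0. If they contribute 1, both arm means sit just above 1, and their ratio is close to 1 however well the vaccine works.

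At stake is one exploratory estimate of VE on symptom duration and severity. Two programmers could follow 6.8.3 and report very different values.

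**Working it through.** **Inputs**

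- Randomised: "Approximately 30,000 participants will be randomized with the following assumptions" (Protocol 9.3), allocated 1:1.
- Excluded from the PP population: about 15% (Protocol 9.3).
- Planned cases: 151. Six-month incidence 0.75% on placebo and 0.30% on vaccine, VE 60% (Protocol 9.3, Table 6).
- PP cases at the primary analysis: 196 (SAP Part A 6.4.2.2).
- Reported VE: 94.5%, given with 95 cases at the interim analysis (SAP Parts B and C, Introduction). Applying it to 196 cases is an illustration.

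**The plan's own case count.** Section 6.8.3 states no figure, but the 151 cases drive the share of positive scores. With HR 0.4 against 0.7, 1-sided alpha 0.025 and 90% power, let p0 = 0.7/1.7 and p1 = 0.4/1.4. Then D = [1.960·√(1/(p0(1−p0))) + 1.282·√(1/(p1(1−p1)))]² / [ln(0.4/0.7)]² = 148.5. Multiplying by 1.014 for the Lan-DeMets O'Brien-Fleming interim looks gives 150.6, which agrees with 151.

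**Share of positive scores.** The PP Set is 30,000 × 0.85 = 25,500.

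| Cases | Positive share | Zero share |
|---|---|---|
| 151 (planned) | 0.59% | 99.41% |
| 196 (primary analysis) | 0.77% | 99.23% |
| 500 (assumed) | 1.96% | 98.04% |
| 1,000 (assumed) | 3.92% | 96.08% |
| 2,000 (assumed) | 7.84% | 92.16% |

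The last three rows are assumptions, because the case count at the final blinded analysis is not in the documents.

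**Cut points.** The 75th percentile is 0 unless more than 25% of the PP Set scores above 0, which is more than 0.25 × 25,500 = 6,375 people. Four separate groups need more than 75%, or more than 19,125. Every row of the table is far below both limits, so all three cut points are 0.

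**Resulting code with 196 cases.** The 25,304 zeros exceed none of the cut points and take code 1. The 196 cases exceed all three and take code 4. If ties are given mean ranks instead, the codes are 2 and 4. Either way there are two values.

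**VE from the ratio of mean codes**

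- Planned rates, codes 1 and 4: placebo 1 + 3 × 0.0075 = 1.0225; vaccine 1 + 3 × 0.0030 = 1.0090; VE = 1 − 1.0090/1.0225 = 1.3%.
- Planned rates, codes 2 and 4: 1 − 2.006/2.015 = 0.4%.
- 196 cases at VE 94.5%, split 10 and 186 over 12,750 per arm, codes 1 and 4: 1 − (1 + 3 × 10/12,750)/(1 + 3 × 186/12,750) = 1 − 1.0024/1.0438 = 4.0%. With codes 2 and 4 it is 1.4%.
- 1,000 assumed cases at VE 94.5%, split 52 and 948: 17.2%, or 6.5% with codes 2 and 4.

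**Alternative coding.** Quartiles among positive scores, with everyone else at 0, gave groups of 49, 50, 49 and 48 for 196 cases in one simulated data set at case VE 60%. The ratio-of-means VE was 0.57 to 0.58 at a case VE of 60%, and 0.94 with 196 cases at 94.5%. These are single simulated data sets with an assumed lognormal score among cases; the zero cut points above do not depend on that assumption.

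**The case against.** The strongest reply is that 6.8.3 is incomplete rather than wrong. Daily grading belongs to the Convalescent Period, and Protocol 8.1.3 says: "If the participant has a negative result for SARS-CoV-2 from the Day 1 Illness Visit, the participant will exit the Convalescent Period". Graded scores therefore exist largely for confirmed cases. It is natural to rank those from 1 to 4, pool the two groups for the cut points, and let everyone else contribute 0. The burden-of-disease and burden-of-infection scores use the same model with 0 for the unaffected. On that reading the quartiles form normally and the estimate tracks VE against cases. This may well be what was meant. It still needs words that 6.8.3 lacks and that 6.8.1 supplies when it wants a case-only analysis.

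Three further points on that side stand:

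- A reader might infer that the plan cannot show VE on symptom burden at all. The documents do not support that. The raw-mean formula in 6.8.3 does not use the quartile code, and Protocol 9.5.4 separately assesses symptomatic days among participants with COVID-19.
- A reader might infer that the model would return nothing. It would not: a two-valued variable can be fitted, and the arms can still be compared on case status.
- The 1.3% and 4% figures hold only if non-cases take code 1, which 6.8.3 does not state in so many words.

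Test-negative illnesses with some graded symptoms could raise the positive share. Their number is not given. They would have to bring it above 25% to move even one cut point.

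**Conclusion.** The point holds for the quartile model only. Applied as written to the whole PP Set, the rule gives cut points of 0, 0 and 0 and a dependent variable that records case status and nothing about duration or severity. That result is insensitive to incidence up to 25% of the PP Set. The near-zero VE (about 1.3% at the planned rates, about 4% with 196 cases and VE 94.5%) also rests on coding non-cases 1, and it would grow with a larger case count.

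The consequence is minor. The analysis is exploratory and optional in its wording, it lies outside the multiplicity sequence, and the primary efficacy conclusion is unaffected. SAP Parts B and C (section 3.4) lists this endpoint as already evaluated for Part A, so what remains is to establish what was actually done.

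**What to change.** State in 6.8.3 the population in which cut points are taken, the code for a score of 0 and the tie rule. Either of two codings would do:

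- Use the raw summed score, with 0 for non-cases, as the dependent variable. This puts the model on the same scale as the VE formula in that section. The raw score may be skewed: in the single simulated data sets at case VE 60%, the raw-mean VE was 0.57 with 151 cases and 0.46 with 196.
- Cut quartiles among positive scores only, code them 1 to 4 and code everyone else 0, in line with Tables 7 and 8. This limits the influence of a few long illnesses.

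The cost is one sentence and one derivation. Because Part A is reported complete, the sponsor should confirm which coding produced the reported result, document it, and rerun this one analysis if the quartiles were cut over the whole PP Set.

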6.8.4. Vaccine Efficacy Against All-cause Mortality

To evaluate VE against all-cause mortality, the same Cox PH model described above based on the PP Set, mITT Set, and FAS will be used. Death, regardless of cause, from randomization will be included. Time to death will be calculated as date of death – date of randomization + 1. At the final analysis of blinded data, subjects with no documented death will be censored.

6.8.5. Vaccine Efficacy Against COVID-19 Over Time

For exploratory analysis of the VE on the COVID-19 primary endpoint over time, to assess if there is any time trend of the effect of the vaccine, e.g. if the effect of the vaccine is waning over time during the follow-up, an extended Cox model with an addition of a covariate incorporating interaction of time by treatment group may be carried out.

For exploratory analysis of the VE on the COVID-19 primary endpoint over time, the instantaneous hazard ratio (mRNA-1273 vs. placebo) of the endpoint may be estimated with pointwise and 95% confidence intervals, using nonparametric kernel smoothing estimation of each of the mRNA-1273 and placebo arm hazard functions over time, using the method of Gilbert *et al.* ([Gilbert, 2002](#)) with optimal bandwidths selected using the analytical formula in Andersen *et al.* ([Andersen, 1993](#)). At each interim analysis, a plot of the hazard ratio results, as well as plots of the point estimates and pointwise and simultaneous 95% confidence interval estimates for the treatment-arm specific hazard functions, may be provided.

6.8.6. Durability of Vaccine Efficacy Against COVID-19

Durability of vaccine efficacy will be assessed by the incidence rate of COVID-19 by time periods.

As an exploratory analysis to assess durability of VE against the primary endpoint, covariate adjustment method based on cumulative incidence may be used. Cumulative incidence VE may be assessed using a parameter $VE_{CI}(0 - t)$, defined as one minus the ratio of cumulative incidences (mRNA-1273 vs. placebo) of the COVID-19 endpoint over

follow-up through time t post enrollment. All times t ranging from 0 to t^* will be considered, where t^* is defined as the final time through which at least 1,000 subjects are at risk for the COVID-19 endpoint. The cumulative incidence for each vaccination group will be estimated using a covariate adjustment method based on [Zeng \(2004\)](#) that makes use of baseline subject information. These covariates will include demographic information such as age, sex, and race/ethnicity, and stratification factor at randomization. The most useful covariates to adjust for in producing potential efficiency gains are potential modifiers of VE.

The covariate adjustment method that will be used is more robust than unadjusted approaches (e.g., the Kaplan-Meier estimator), as it yields valid inferences even in cases in which loss to follow-up is informative, provided within each intervention arm the possible relationship between censoring and the COVID-19 endpoint can be explained by observed baseline covariates. Unadjusted methods, in contrast, can give biased answers in this setting, which manifests as 95% confidence intervals that contain the true VE less than 95% of the time, or as tests of the null $H_0: VE \leq 30\%$ that reject with probability greater than the specified type 1 error level. Also, the covariate adjustment method often results in more precise estimates when available baseline covariates (e.g. stratification factor at randomization) are predictive of the COVID-19 endpoint, thereby yielding tighter confidence intervals for the cumulative VE and higher-powered tests of the null hypothesis. This efficiency gain may be especially pronounced in settings where the randomization is not stratified on factors such as age category or trial site.

The estimator for the survival function in arm v (mRNA-1273 or placebo) that adjusts for baseline covariates L is implemented using the following steps:

1. (a) Using only data from arm v , fit a main terms Cox regression to estimate the hazard of the COVID-19 endpoint conditionally on L . Refer to the fitted vector of coefficients as $\hat{\beta}$.

- (b) Repeat step (a), but estimate the hazard of *censoring* conditionally on L . Refer to the fitted vector of coefficients as $\hat{\gamma}$.
2. For given coefficient $\hat{\alpha}$ ($= \hat{\beta}$ or $\hat{\gamma}$) and a given covariate value ℓ , let $f_{\hat{\alpha}}(\ell)$ denote the $j \in 1, \dots, 4$ for which $q_{\hat{\alpha},j-1} < \hat{\alpha}^\top \ell \leq q_{\hat{\alpha},j}$, where $q_{\hat{\alpha},1}, q_{\hat{\alpha},2}, q_{\hat{\alpha},3}$ denote the empirical quartiles of $\hat{\alpha}^\top L$ in arm v and $q_{\hat{\alpha},0} = -\infty$ and $q_{\hat{\alpha},4} = \infty$.
 3. Using only data from arm v , fit a stratified Kaplan Meier using the COVID-19 endpoint as outcome within all non-empty strata of $(f_{\hat{\beta}}(L), f_{\hat{\gamma}}(L))$ – there will be at most 16 such strata. If any strata are empty, estimate the survival function within those strata as the constant function 1.
 4. Estimate the arm-specific survival function by taking a weighted average across the 16 strata, where each stratum-specific survival function receives weight equal to the empirical probability of a randomly selected Subject (from either the vaccine or placebo arm) having baseline covariates belonging to that stratum.

Estimates of the arm-specific cumulative incidences and cumulative incidence VE are obtained by transforming the estimated arm-specific survival functions. Missing covariates will be accounted for using median imputation, which preserves the randomization of treatment even given imputed covariates.

The validity of this estimator relies on the condition that, within all strata of L , there must be a positive probability that a Subject will have follow-up through time t^* . As such, covariates such as trial site should not be included in if the enrollment timeline is such that this condition fails to hold.

Two-sided Wald-based 95% confidence intervals for a log-transformed cumulative incidence ratio estimate will be provided, and these intervals will be transformed to yield intervals for $VE_t(0-t)$, $t \in [0, t^*]$. Accompanying uniform confidence bands, constructed using the multiplier bootstrap with Rademacher weights (Kosorok 2007), will also be provided. The covariate-adjusted arm-specific cumulative incidence estimates will also be plotted over time, with confidence intervals and uniform confidence bands defined

by transforming a Wald interval for a complementary log-log transformation of the corresponding survival functions.

6.9. Summary of Protocol Safety Review and Data Safety Monitoring Board

6.9.1. Protocol Safety Review Team

A Protocol Safety Review Team (PSRT) will be formed to review interim and cumulative blinded safety data on a regular basis with a remit to escalate concerns to the DSMB. The PSRT will be composed of the study's three coordinating investigators and representatives from Moderna, National Institute of Allergy and Infectious Diseases (NIAID), Biomedical Advanced Research and Development Authority (BARDA), and the CRO. The PSRT composition, its remit, and the routine and systematic procedures for safety review and oversight of blinded interval and cumulative data during the mRNA-1273 P301 study by the PSRT is documented in the Moderna mRNA-1273 P301 Protocol Safety Review Team Charter.

